### **2.3.3 Case Report Forms and Evaluations**

The electronic case report form (eCRF) is the primary data collection instrument for the study. All data requested on the eCRF must be recorded. All missing data and errors must be explained by edit checks.

If a correction is required for an eCRF, the time and date stamps track the person entering or updating eCRF data and creates an electronic audit trail to reflect the reason for the change.

If the electronic data cannot be directly entered onto the eCRFs, these data should be created, imported, stored and maintained appropriately to ensure data and system security.

#### **2.3.3.1 *Eligibility Evaluation CRFs***

The Eligibility Evaluation CRF includes the Inclusion/Exclusion Checklist.

#### **Inclusion/Exclusion Checklist**

The investigator or designee will review the inclusion and exclusion criteria. This form includes the inclusion and exclusion criteria checklist or validation.

### **2.3.3.2 *Protocol Deviation CRF***

This form will be used to document any protocol deviations in the study. Please see Section 2.6 and Protocol Deviation CRF for additional information regarding Protocol Deviations.

### **2.3.3.3 *Subject Discontinuation CRF***

This form will be used to document a subject's reason for exiting the study. Please see Section 2.5 for additional information regarding Subject Discontinuation.

### **2.3.3.4 *Adverse Event CRF***

All adverse events and complications will be recorded and reported on the Adverse Event CRF. Serious adverse events must be reported to the Sponsor within 24 hours, but no later than 10 days after made aware of the event.

## **2.4 *Classification of Adverse Events and Reporting of Adverse Events***

Serious adverse events must be reported to the Sponsor within 24 hours of becoming aware of the event, but no later than 10 days after the event. The Investigator is responsible for reporting adverse events to their individual IRBs.

Serious adverse event is defined as:

- Death
- A serious deterioration in the health of the patient that results in a life-threatening illness or injury
- A permanent impairment of a body structure or body function
- In-patient hospitalization or prolongation of existing hospitalization
- Medical or surgical intervention to prevent permanent impairment to body structure or function
- Fetal distress, fetal death or congenital abnormality or birth defect.

### **2.4.1 *Adverse Event Reporting***

Adverse event reporting will comply with the regulations of the local IRB.

## **2.5 *Subject Withdrawal***

An enrolled subject is considered 'withdrawn' from the study if their participation in the study is discontinued for any reason after enrollment. Possible reasons for withdrawal include:

- Eligibility Criteria not met
- Investigator judgment

If a subject withdraws from the study, a Subject Discontinuation CRF will be completed.

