## 2.2.2 Inclusion Criteria

Candidates for this study must meet all of the following Inclusion criteria:

1. 18 years of age or older;
2. Admission to emergency department requiring immediate medical attention which is presumed to be cardiac or cardiopulmonary related and considered 2nd or 3rd tier priority in triage system. Symptoms including:
  - Shortness of breath
  - Skin pallor consistent with cardiopulmonary complications
  - Chest pain
  - Rapid or irregular heartbeat

And any symptoms considered to be cardiac or cardiopulmonary-related by the investigator

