## 2.2.3 Exclusion Criteria

Candidates will be excluded from the study if any of the following conditions are present:

1. Pregnant or suspected pregnancy;
2. Significant trauma
3. Do Not Resuscitate order
4. Known as ward of the state

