### 2.3.1 Subject Enrollment

Subjects are enrolled in this study when they have:

- Met all eligibility criteria.

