### **3.7 Sample Size**

Approximately 760 subjects are planned to be enrolled in the study to provide 634 subjects in the final analysis.

When the sample size is 634, the logistic regression test of  $\beta=0$  ( $\alpha = 0.050$  two-sided) will have 80% power to detect a  $\beta$  of 0.747 (an odds ratio of 2.111); this assumes that one normally distributed covariate  $x$  is being added to the model after adjustment for prior covariates, that its multiple correlation with covariates already in the model is 0.500 and, that the proportion of successes at the mean of  $x$  is 0.050.

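### Section 2.5 allows enrolled subjects to be withdrawn on the investigator's judgment at any point in the 72-hour outcome window, and nothing says how their outcomes are then collected or analysed

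*Combined protocol and SAP*

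**What the plan says.** Under Section 2.1.2, subjects are enrolled on arrival at the ED and followed for 72 hours. Section 2.3.1 makes enrollment conditional on having "Met all eligibility criteria". Section 2.5 then treats a subject as withdrawn "if their participation in the study is discontinued for any reason after enrollment". It offers two possible reasons, "Eligibility Criteria not met" and "Investigator judgment", and defines neither further. Its only consequence is a form: "If a subject withdraws from the study, a Subject Discontinuation CRF will be completed".

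Four other places bear on the point:

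- The Schedule of Events (Section 2.3) checks the inclusion and exclusion criteria at admission only. It puts discharge and withdrawal in one shared column.
- Section 3.5 plans no blinding.
- Section 3.6 bases the primary analysis on observed data. It adds two sensitivity analyses in which subjects with missing data are all counted as having no event, or all as having one.
- Section 3.7 states: "Approximately 760 subjects are planned to be enrolled in the study to provide 634 subjects in the final analysis".

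Deletion of data is prescribed only where consent is not obtained (Sections 1.2.1 and 5.2.2).

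**The concern.** Section 1.1 says the study will investigate the algorithm's sensitivity and specificity, and Section 3.2 plans an ROC area. These describe performance in patients as they present. If a subject can leave on the judgment of someone who already knows the work-up and the course, the remaining sample may be selected on the result being measured.

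An observational study gives no evident reason for such an exit, because there is no study treatment to stop. The loss may also be permanent. Withdrawal shares a column with discharge as the last data-collection point, and Section 2.3.3.3 describes the discontinuation form as recording why a subject left the study. A 72-hour outcome that was never collected cannot be recovered at analysis. With few expected events, a handful of withdrawals is enough to matter.

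**Working it through.** No figure in the plan is made wrong by this point, so the arithmetic shows direction and size only.

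**The plan's own numbers.** The 634 in Section 3.7 follows from Hsieh's formula for one normal covariate:

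n = [z(0.975) + z(0.80)·exp(−b²/4)]² × (1 + 2Pδ) / (P·b²) / (1 − R²), with δ = [1 + (1 + b²)·exp(5b²/4)] / [1 + exp(−b²/4)].

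With b = 0.747 and P = 0.05, this is 317.1 before the correlation adjustment. Dividing by (1 − 0.5) gives 634.2. (This enters 0.500 as the squared multiple correlation, which is a separate matter.) The allowance between enrollment and analysis is 760 − 634 = 126, or 126/760 = 16.6%. The plan gives no reason for it.

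**Inputs for the illustration.** 634 analysed and 5% events (Section 3.7, where 5% is the planning value at the mean of the covariate). Sensitivity 0.88 and specificity 0.68 (prior chest-pain study, Section 1.1). The number of withdrawals is assumed, because the documents give none.

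**Starting table.** Events: 0.05 × 634 ≈ 32, of which 0.88 × 32 ≈ 28 true positives and 4 false negatives. Non-events: 602, of which 0.68 × 602 ≈ 409 true negatives and 193 false positives. Sensitivity = 28/32 = 0.875; specificity = 409/602 = 0.679.

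**Selective loss.**

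- Lose 2 false negatives: 28/30 = 0.933.
- Lose 4 true positives: 24/28 = 0.857.
- Lose 40 false positives: 409/562 = 0.728.
- ROC area, taking the single cut-off value (sensitivity + specificity)/2: start (0.875 + 0.679)/2 = 0.78. Losing 2 false negatives and 40 false positives gives (0.933 + 0.728)/2 = 0.83. Losing 4 true positives gives (0.857 + 0.679)/2 = 0.77.

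**Proportionate loss.** Lose 60 non-events as 19 false positives and 41 true negatives: 368/542 = 0.679, unchanged. Lose 8 events as 7 true positives and 1 false negative: 21/24 = 0.875, unchanged. So loss related to outcome alone leaves both measures intact; the loss must also be related to the score. Loss related to score alone moves them in opposite directions: losing about a quarter of low scores (1 false negative, 102 true negatives) gives 28/31 = 0.903 and 307/500 = 0.614.

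**Range for the event rate.** The prior study's PPV of 0.195 implies a prevalence of 1/[1 + 0.88 × 0.805/(0.195 × 0.32)] = 0.081. At 634 that is about 51 events (45 true positives, 6 false negatives) and 583 non-events (396 true negatives, 187 false positives). The same losses give 45/49 = 0.918 and 41/47 = 0.872 (from 45/51 = 0.882), and 396/543 = 0.729 (from 396/583 = 0.679).

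**What Section 3.6 would show if it applied.** High scores are (28 + 193)/634 = 35%. Suppose 20 withdrawn subjects have the same mix, 7 high and 13 low. Counting all as events gives sensitivity 35/52 = 0.67; counting none leaves 0.88. At the extreme of all 126 (44 high, 82 low), the all-event result is 72/158 = 0.46. The bracket works but widens quickly.

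**The case against.** A reader might infer that the plan lets sites remove a subject because the final diagnosis proves non-cardiac, or because a "Do Not Resuscitate order" is written on day 2. The text does not support this.

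- The Schedule of Events checks eligibility at admission only.
- Section 2.2.3 speaks of candidates, meaning people not yet enrolled.
- Section 2.2.2 requires only a cause "which is presumed to be cardiac or cardiopulmonary related", and a later diagnosis does not undo a presumption. The protocol records both an ED and a final diagnosis, so it expects them to differ.
- The natural meaning of the eligibility reason is an enrollment error found later, and correcting that is legitimate.
- The late-order example is also weak for the primary outcome, because death is not listed separately in Section 3.2.

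A reader might also infer that withdrawn subjects are excluded, so that accuracy is inflated. Section 2.5 does not say so. Where deletion is meant, for missing consent, the protocol states it. For revoked authorization, Section 5.5.1 keeps what has been collected. Section 3.6 may already bracket the loss. Direction is not fixed either: most events are true positives, so losing events could lower sensitivity. No readable text shows that investigators see the score. PPV is not a planned measure. Nothing ties the 126 to withdrawals.

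All of this stands, and it narrows the point. It does not close the investigator-judgment route, which is undefined and open throughout the window. Nor does it supply a rule for the outcomes of those who leave. A link with the score does not require seeing it, since Section 1.1 says the algorithm uses vital signs and mental status, which also inform clinical judgment.

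**Conclusion.** The point holds as a conditional risk. Section 2.5 leaves a discretionary exit, open to unblinded investigators during outcome ascertainment, and the plan neither secures nor assigns the outcomes of those who take it. Bias needs two things the documents do not establish: withdrawals related to score as well as course, and loss of those subjects from the analysis. If both occur, sensitivity could move from 0.88 to between about 0.86 and 0.93 with two to four withdrawals, and specificity from 0.68 to 0.73 with 40. The ROC area would move with them, up or down. These sizes assume 634 analysed, about 32 events and the prior study's accuracy; at 8.1% events the sensitivity shifts are somewhat smaller. The documents do not show that such withdrawals are expected or that results would be inflated. This is a cheap improvement.

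**What to change.** - **Section 2.5:** remove investigator judgment as a reason to drop a subject from this non-interventional study. Limit the eligibility reason to facts that existed at ED admission, consistent with the admission-only check in the Schedule of Events, and say that a later diagnosis or later order is not a reason.
- **Section 3.6:** state that all enrolled, consented subjects stay in the primary analysis with their observed 72-hour outcome. State that any withdrawn subject without an outcome counts as missing in both sensitivity analyses.

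The consent rule in Section 5.2.2 is untouched. The cost is a few sentences, with no new visits or data items. One small downside is that some subjects with a non-cardiac final diagnosis stay in, so accuracy may look slightly less favourable.

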## **2.6 Protocol Deviations**

An Investigator shall notify the sponsor and reviewing IRB of any deviations from the study protocol that are done to protect the life or physical well-being of a subject. Such notice shall be given as soon as possible, but no later than 5 working days after the deviation occurred.

A protocol deviation is defined as a deviation from the study protocol.

Protocol deviations will be documented on a Protocol Deviation CRF.

# **3 Statistical Analysis**

## **3.1 Introduction**

The primary objective is to verify an existing prediction algorithm of cardiopulmonary events. The secondary objective is to assess the prediction algorithm with regard to the frequency of cardiopulmonary events.

Standard summary statistics will be calculated for relevant study variables. For continuous variables, summary statistics will include means, medians, standard deviations and 95% confidence intervals around the means. Categorical variables will be summarized using counts and percentages. Statistical analyses will be conducted in SAS version 9.1 or above (SAS Institute, Cary, N.C.) or another statistical analysis package.

## **3.2 Primary Outcome Measure**

The primary outcome measure is the occurrence of cardiopulmonary events. It will be measured as the occurrence of any cardiopulmonary event, within 72 hours of presentation to the ED, including:

Cardiac arrest

Sustained ventricular tachycardia (VT)

Hypotension requiring inotropes or intraaortic balloon pump (IABP) insertion

Intubation or mechanical ventilation

Complete heart block

Bradycardia requiring insertion of a pacing wire or external pacing, and

Percutaneous coronary intervention (PCI) or coronary artery bypass surgery (CABG).

For the primary outcome measure of occurrence of cardiopulmonary events, binary logistic regression will be used to estimate the probability that a cardiopulmonary

event has occurred given the values of explanatory variables, given by the following equation:

- $Y$  is the primary outcome measure  
 $Y_i = 1$  if a cardiopulmonary event has occurred  
 $Y_i = 0$  if there is no cardiopulmonary event
- $\pi_i$  = the probability of a cardiopulmonary event
- $X = (X_1, X_2, \dots, X_k)$  being the set of explanatory variables

*Model:*

$$\text{logit}(\pi_i) = \beta_0 + \beta_1 x_{i1} + \dots + \beta_k x_{ik}$$

A Receiver Operating Characteristic Curve will be constructed and the area under the curve will be calculated to assess the model sensitivity.

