A novel algorithm for determining risk of acute cardiac complications, including cardiac arrest, for patients presenting to the ED has recently been reported. Unlike prior risk stratification tools that relied on basic vital sign data, this algorithm utilizes multiple metrics of heart rate variability (HRV) as well as a machine learning approach to solve the risk classification problem. The algorithm requires the collection of vital sign data, patient mental status, and *at least* 5 minutes of continuous electrocardiography (to calculate HRV metrics). It was shown to be more accurate than MEWS in predicting cardiac arrest within 72 hours of admission to hospital. Furthermore, the algorithm has been used to predict serious complications (mortality, cardiac arrest, ventricular tachycardia, hypotension requiring inotropes or intra-aortic balloon pump (IABP) insertion, intubation or mechanical ventilation, complete heart block, bradycardia requiring pacing, and recurrent ischemia requiring revascularization) within 72 hours in patients presenting to the ED with chest pain. In this patient population, a score of 4 or higher from the algorithm had a sensitivity of 0.880, specificity of 0.680, positive predictive value of 0.195, and a negative predictive value of 0.985 which was better than using ST elevation/depression and troponin in predicting complications within 72 hours. The primary limitation of the algorithm is that it has been developed and tested in Singaporean patients. Verification of the results of the studies using this algorithm in other patient cohorts is required. As such, the proposed study will investigate the sensitivity and specificity of the algorithm.

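### The planned performance measures cover ranking and classification only, so the study will not show whether the event risk seen at a given algorithm score carries over to the new population

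*Combined protocol and SAP*

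**What the plan says.** Section 3.1 states the aim: "The primary objective is to verify an existing prediction algorithm of cardiopulmonary events". Section 3.2 then says that "binary logistic regression will be used to estimate the probability" of the 72-hour composite, given covariates described only as "being the set of explanatory variables"; the algorithm's score is not named among them. The one performance measure follows: "A Receiver Operating Characteristic Curve will be constructed and the area under the curve will be calculated to assess the model sensitivity".

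Section 1.1 (Background) adds that "the proposed study will investigate the sensitivity and specificity of the algorithm". It also reports results from an earlier cohort of ED patients with chest pain. At a score of 4 or higher, sensitivity was 0.880 and specificity 0.680, with a "positive predictive value of 0.195, and a negative predictive value of 0.985". It gives the reason for the study: the algorithm has so far been developed and tested only in Singaporean patients.

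Section 3.7 bases the 634 analysed subjects on a test of whether one regression coefficient is zero. That is a test of association.

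Nowhere do the documents plan predictive values in the new cohort, an observed event proportion by score, or a calibration intercept, slope or plot. They set no criterion for calling the algorithm verified.

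**The concern.** A score can be checked in a new population in two respects. One is whether it still orders or classifies patients correctly. The other is whether a patient with a given score has about the same event risk as before. AUC, sensitivity and specificity address only the first. The fitted probabilities in Section 3.2 do not address the second, because they are re-estimated from the study's own data and no comparison with any earlier figure is planned.

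The study exists because the algorithm is being moved to a different population, where a change in baseline event rate is plausible. If discrimination replicates and the report says only that the algorithm was verified, a reader could assume that the earlier predictive values also apply. The planned analysis gives no direct evidence on that.

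**Working it through.** **Inputs.** From Section 1.1: sensitivity 0.880, specificity 0.680, PPV 0.195, NPV 0.985 at a score of 4 or higher. From Section 3.7: 634 analysed subjects, event proportion 0.050 at the covariate mean, coefficient 0.747, multiple correlation given as 0.500.

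**1. The plan's own figures.**

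- *Sample size.* With one normal covariate, Hsieh's 1989 formula is n = [1.960 + 0.842·exp(−b²/4)]²·(1 + 2Pδ) / (P·b²) / (1 − R²), where δ = [1 + (1 + b²)·exp(5b²/4)] / [1 + exp(−b²/4)]. With b = 0.747, P = 0.05 and R² = 0.500, n = 634.2, against the stated 634. (The match needs 0.500 to be the squared correlation; this does not affect the present point.)
- *Predictive values.* PPV = 0.88p / [0.88p + 0.32(1 − p)]. Setting PPV = 0.195 gives p = (0.195 × 0.32) / (0.88 × 0.805 + 0.195 × 0.32) = 0.081. NPV at that rate is 0.68 × 0.919 / (0.68 × 0.919 + 0.12 × 0.081) = 0.985, as stated. The published figures agree with each other and imply an event rate of 8.1%.

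**2. Same sensitivity and specificity, different event rate.** The rates other than 8.1% are assumptions. 5% is the Section 3.7 input used as if it were the overall rate. 6.2% is the average of the logistic curve with 5% at the mean, slope 0.747 and a standard normal covariate.

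| Event rate | Risk at score ≥ 4 | 19.5% divided by that risk |
|---|---|---|
| 5% | 0.044 / (0.044 + 0.304) = 12.6% | 1.54 |
| 6.2% | 0.0546 / (0.0546 + 0.3002) = 15.4% | 1.27 |
| 8.1% | 19.5% | 1.00 |
| 10% | 0.088 / (0.088 + 0.288) = 23.4% | 0.83 |

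Sensitivity and specificity replicate exactly in every row, while the risk at the cut-off does not.

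**3. What AUC and refitting show.** 2,000 data sets of 634 subjects were simulated per scenario, with intercept logit(0.05) and slope 0.747. The miscalibration scenarios are assumed.

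| Risk assigned before refitting | AUC | Mean predicted / observed | Same ratio after refitting |
|---|---|---|---|
| Correct | 0.70 | 1.02 | 1.00 |
| Odds doubled | 0.70 | 1.88 | 1.00 |
| Odds halved | 0.70 | 0.54 | 1.00 |

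AUC does not move, and the refitted model always returns the study's own event rate.

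**4. What a table by score would deliver at 634 subjects.**

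- *5% rate:* 31.7 events, of which 0.88 × 31.7 = 27.9 score 4 or higher, with 0.32 × 602.3 = 192.7 non-events. That is about 28/221, exact 95% CI 8.6% to 17.8%, which excludes 19.5%. Below 4: about 4 events.
- *6.2% rate:* 39.3 events, of which 34.6 score 4 or higher, with 0.32 × 594.7 = 190.3 non-events. That is about 35/225, exact 95% CI 11.1% to 21.0%, which includes 19.5%. Below 4: about 5 events.

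If the algorithm outputs a probability, the same simulations give a standard error of about 0.17 for calibration-in-the-large (logit scale) and about 0.24 for the calibration slope. A test of calibration-in-the-large would have about 96% power to detect halved odds and over 99% to detect doubled odds.

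**The case against.** The strongest case against has four parts.

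- **No risk is attached to the score.** Section 1.1 describes a classification tool with a cut-off and never says that it outputs a probability. The PPV and NPV are results from one cohort and depend on its event rate. This stands. A reader might infer that 19.5% and 1.5% are risks the algorithm claims, and that a different figure would prove it wrong. The documents do not support that.
- **The benchmark is not like for like.** The earlier figures come from chest-pain patients, while Section 2.2.2 also admits shortness of breath, pallor and rapid or irregular heartbeat. The earlier composite included mortality, and revascularization for recurrent ischemia. The composite in Sections 2.1.5 and 3.2 does not list death as its own component and counts PCI or CABG without that restriction. This also stands: a gap could come from case mix or endpoint definition.
- **Ranking is what triage needs.** Section 1.1 frames triage as finding the patient at highest risk, and names sensitivity and specificity as the aim. So AUC is relevant. It does not follow that it is enough to verify a score in a new population.
- **A shift would not be invisible.** Section 3.1 summarizes categorical variables by counts and percentages, so the event rate should be reported. Together with sensitivity and specificity at the same cut-off, it yields the PPV. This stands in part: the shift could be worked out afterwards, but no such comparison is planned and Section 3.2 does not tie its model to the existing score.

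**Conclusion.** The gap is real and modest. The plan measures discrimination and classification, and does not set the observed risk at a given score beside any earlier figure. A favourable result would verify discrimination only.

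The size is illustrative: 12.6% or 15.4% at a score of 4 or higher, against 19.5%, which is an overstatement of 1.54 or 1.27 times. It rests on sensitivity and specificity carrying over unchanged, and on event rates taken from planning inputs, not from expected cohort rates. The 6.2% further assumes a standard normal covariate and takes the detectable coefficient as the true slope. At a rate above 8.1% the difference would run the other way.

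A reader might go further and say that the plan would declare an algorithm with wrong absolute risks verified. The documents do not support this. They set no verification rule, they do not say that the algorithm assigns risks, and the earlier predictive values come from a different case mix and composite. Agreement with 19.5% and 1.5% would not be a fair test of the algorithm.

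**What to change.** Add to Section 3.2, for the algorithm's existing score without refitting:

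1. The observed 72-hour event proportion with exact 95% CI by score band, including PPV and NPV for 4 or higher versus below 4. Show the published 0.195 and 0.985 beside them as descriptive context, show the chest-pain subgroup separately, and state the population and endpoint differences.
2. If the algorithm outputs a probability, the calibration intercept and slope with 95% CIs and a calibration plot.
3. A sentence saying that a conclusion based on AUC, sensitivity and specificity verifies discrimination only. Agreement with 19.5% and 1.5% should not be made a criterion for verification.

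The cost is SAP wording and one more table or plot, with no extra subjects or procedures. It does require the score to be computed for each subject, as any verification of the existing algorithm would. The drawback is imprecision: about 28 to 35 events are expected at 4 or higher and about 4 to 5 below, and the chest-pain subgroup will have fewer still.

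### The aim is to verify an existing algorithm, but Section 3.2 plans the AUC of a refitted logistic model with unnamed predictors, and sets no cut-off or confidence interval for the algorithm's own accuracy

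*Combined protocol and SAP*

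**What the plan says.** Section 3.1 restates the aim: "The primary objective is to verify an existing prediction algorithm of cardiopulmonary events". Section 1.1 explains that the algorithm was developed and tested in Singaporean patients and needs checking elsewhere, and concludes: "As such, the proposed study will investigate the sensitivity and specificity of the algorithm". It also reports an earlier study in chest-pain patients in which "a score of 4 or higher from the algorithm had a sensitivity of 0.880, specificity of 0.680".

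Section 3.2 turns the aim into an analysis. There "binary logistic regression will be used to estimate the probability that a cardiopulmonary" event has occurred, with X1 to Xk "being the set of explanatory variables". No member of that set is named. Performance is then covered in one sentence: "A Receiver Operating Characteristic Curve will be constructed and the area under the curve will be calculated to assess the model sensitivity".

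Section 3.7 sizes the study for a test of one coefficient ("When the sample size is 634, the logistic regression test of" β = 0). It assumes that one unnamed normal covariate "is being added to the model after adjustment for prior covariates, that its multiple correlation with covariates already in the model is 0.500".

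Within Section 3 the algorithm appears only where Section 3.1 restates the objectives. The only confidence intervals mentioned are those around means of continuous variables. The cut-off of 4 is not carried over from Section 1.1. Section 3 shows no redaction that could hide these items.

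**The concern.** Verifying an existing score means taking the score as it stands and measuring how well it separates patients with and without events. A logistic model fitted to the study data does that only if the score is its sole predictor. With other predictors in the model, the coefficients are estimated afresh and the AUC describes the combination. Two analysts who both followed Section 3.2 could therefore report AUCs of different objects, and one of them need not describe the algorithm at all.

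The second gap does not depend on how the model is read. An AUC summarises discrimination over all cut-offs; it is not a sensitivity. The sensitivity and specificity named in Section 1.1 have no cut-off fixed in advance and no stated precision, so nothing prevents a cut-off from being chosen after the curve is seen.

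The β = 0 test in Section 3.7 does not fill either gap. If the tested covariate is the score, the test shows whether the score adds information to the other covariates. The section does not say that it is the score, and a non-zero coefficient does not measure accuracy.

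**Working it through.** **1. Reproduce the planned sample size.** Inputs from Section 3.7: b = 0.747, P = 0.05, two-sided α = 0.05, power 80%, correlation term 0.500. The Hsieh (1989) formula for one normal covariate is

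n = [z(0.975) + z(0.80)·exp(−b²/4)]² · (1 + 2Pδ) / (P·b²), with δ = [1 + (1 + b²)·exp(5b²/4)] / [1 + exp(−b²/4)].

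- δ = 2.209 and the bracket is 2.692, so n = 2.692² × 1.2209 / 0.02790 = 317.1 before adjustment for other covariates.
- Dividing by 1 − 0.50 (0.500 taken as R²) gives 634.2, which matches the plan.
- Dividing by 1 − 0.25 (0.500 taken as R) gives 423, which does not.

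R² = 0.50 is therefore used below. The calculation concerns one coefficient; it says nothing about the precision of an AUC, sensitivity or specificity.

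**2. How far the model's AUC can differ from the score's.** Assumptions: score and one other covariate are standard normal with R² = 0.50 between them; the intercept is ln(0.05/0.95); 634 subjects are analysed. The documents do not give the number of predictors, so two is an illustration.

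| Case | Event rate | Events in 634 | Model AUC | Score AUC | Gap |
|---|---|---|---|---|---|
| Score is the only predictor, β = 0.747 | 6.2% | 40 | 0.70 | 0.70 | 0 |
| Score and covariate both β = 0.747 | 9.3% | 59 | 0.81 | 0.79 | 0.02 |
| Score β = 0, covariate β = 0.747 (worst case) | 6.3% | 40 | 0.70 | 0.64 | 0.06 |

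In the worst case, 58% of 3,000 simulated studies of 634 subjects showed a gap above 0.05.

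**3. Precision of the score's own accuracy.** Assume for illustration that the sensitivity of 0.880 and specificity of 0.680 in Section 1.1 carry over. Event counts:

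- 32 is 5% of 634.
- 40 is the marginal count from step 2.
- 51 follows from the prevalence implied in Section 1.1: 0.195 × 0.320 / (0.880 × 0.805 + 0.195 × 0.320) = 0.081, and 0.081 × 634 ≈ 51.

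Exact (Clopper-Pearson) 95% intervals for sensitivity and Hanley-McNeil half-widths (1.96 × SE) at an assumed AUC of 0.70:

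| Events | Sensitivity | Exact 95% CI | AUC half-width |
|---|---|---|---|
| 32 | 28/32 = 0.875 | 0.71–0.96 | 0.10 |
| 40 | 35/40 = 0.875 | 0.73–0.96 | 0.09 |
| 51 | 45/51 = 0.882 | 0.76–0.96 | 0.08 |

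Specificity is estimated much better: 404/594 = 0.680, 95% CI 0.64–0.72.

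**The case against.** The strongest reply is that the plan is underspecified rather than wrong. Section 3 opens by naming the algorithm as the object of both objectives, so the score is a natural candidate for an explanatory variable. X1 to Xk is generic notation, and Section 3.7 is a power assumption, not a definition of the Section 3.2 model. With the score as sole predictor, the AUC is exactly the quantity wanted. This stands: a reader might infer that the planned AUC certainly does not describe the algorithm, and the documents do not settle that. They leave it open, with the wording of Section 3.7 pointing towards several predictors.

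The size also has limits. Taking the 0.500 in Section 3.7 literally as R would give a worst-case gap of 0.10 (0.70 against 0.60), but that reading gives 423 subjects, not 634. The worst case gives the score no effect of its own, which is not the alternative Section 3.7 describes if the score is the added covariate. The nearer case has a gap of about 0.02, small beside the sampling error of the AUC.

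It can also be said that sensitivity and specificity appear as a study aim only in one background sentence, not among the objectives or outcomes, and that an ROC curve shows both at every cut-off. That is true. But the sentence states what the study will investigate, and a curve without a fixed cut-off or intervals does not give a confirmable estimate of either. A reader might go further and infer that a cut-off will be picked after the fact; the plan does not say so, it only leaves room for it.

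**Conclusion.** The point holds as a mismatch between the stated aim and the specified analysis. Under either reading of Section 3.2, the cut-off and the intervals for AUC, sensitivity and specificity are missing. Under the multivariable reading, the AUC also belongs to a newly fitted model and can overstate the algorithm by about 0.02 with equally strong predictors, and by about 0.06 in the worst case. With the score as sole predictor (positive slope) there is no overstatement.

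These sizes rest on two normal predictors, R² = 0.50 and the inputs of Section 3.7. Overfitting with many predictors could enlarge the gap, but the number of predictors is not given, so no figure is claimed for it. Nor do the documents support an inference that the score is not collected: Section 2.3.2.1 is partly redacted and the tablet-app appendix in the table of contents is not in the supplied text.

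It should be settled before analysis, because the main reported result could otherwise fail to answer the primary objective.

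**What to change.** - **Section 3.2, primary analysis:** the AUC with 95% CI of the existing algorithm's score, used as produced and not refitted, plus sensitivity and specificity with exact 95% CIs at one cut-off fixed before the data are analysed. The cut-off of 4 or higher in Section 1.1 is a candidate. It comes from chest-pain patients and a different composite, one that names mortality, which Section 3.2 does not list as a separate item. The choice should therefore be justified.
- **Section 3.2, other models:** label any multivariable model secondary or exploratory and list its predictors.
- **Section 3.7:** name the covariate tested by β = 0 if that test is kept, state whether 0.500 is R or R², and give the expected precision of AUC, sensitivity and specificity.
- **Data:** the sponsor should confirm that the score is stored for each subject.

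The cost is a few sentences, with no new patients or visits if the score is stored. The drawback is visible imprecision: a sensitivity near 0.88 would carry an interval of about 0.71–0.96 with 32 events, or 0.76–0.96 with 51. That imprecision already exists at this sample size; the change only states it. The score's own AUC may also be lower than that of a fitted combination.
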